CES1 Crossover Trial of Clopidogrel and Ticagrelor
NCT03161678
March 5, 2024

STUDY PROTOCOL AND STATISTICAL ANALYSIS PLAN

The purpose of this investigation was to conduct a randomized crossover study of clopidogrel and ticagrelor in participants recruited by carboxylesterase 1 (*CES1*) genotype (G143E and rs7498748). Extensive phenotyping including *ex vivo* platelet aggregometry performed pre- and post-drug administration was performed in order to assess the interaction of genotype and drug choice on on-treatment platelet function. Specifically, we enrolled 89 healthy Amish participants based on *CES1* genotype (17 G143E carriers, 38 rs7498748 minor allele carriers, and 34 controls who did contain the minor alleles of either of these variants). All of these individuals underwent a randomized crossover study of clopidogrel (75 mg per day for 7 d) and ticagrelor (90 mg twice daily for 7 d), with at least a 14-day washout period between drug interventions. Platelet aggregation studies and other clinical information were recorded before and after each intervention.

Home visit to screen for eligibility: A research nurse and an Amish community liaison visited potential research subjects in their homes. The nurse explained the study and obtained informed consent. If a research subject consented, the nurse obtained a medical history and screening laboratory tests to assess eligibility. Briefly, participants were excluded if they were pregnant, currently breastfeeding, had history of a bleeding disorder or major spontaneous bleed, hypertensive, creatinine levels > 2.0 mg/dL, ALT or AST > 2 x the upper limit of normal, hematocrit < 28%, TSH < 0.4 or >5.5 mIU/L, platelet count > 500,000 or < 75,000, currently taking clopidogrel, ticagrelor, prasugrel, or other anti-coagulant, history of cardiovascular disease or diabetes, was taking vitamins or other supplements and was unwilling or could not safely, in the opinion of the study physician, discontinue their use at least 1 week prior to protocol initiation.

Subjects were informed that to participate in this study, they had to discontinue for a period starting 7 days prior to the initial clinic visit any vitamins, supplements and medications that might affect the results of the study. Specifically, if a subject is on medications that may potentially interfere with the planned intervention, he/she was instructed to consult with his/her physician regarding discontinuing such therapy prior to study enrollment. Alternatively, with the subject's permission, the study physician contacted the subject's physician to discuss and obtain permission for medication withdrawal. If in the opinion of the subject's physician and the study physician, discontinuation of medications for the duration of the study did not pose any undue health risks, medications were discontinued one week before the first clinic visit. If a medication required tapering, this commenced two weeks prior to the first clinic visit. Similarly, all vitamins (except daily multivitamins) and other supplements were withdrawn for 7 days prior to the first clinic visit. If the research subject was on anti-platelet medications, these agents were withdrawn 14 days prior to the first clinic visit.

Female research participants were informed that they could not participate in this study if they are pregnant. All female subjects had an assessment of child-bearing potential. Pregnancy status was determined by self-report at the screening visit. A urine pregnancy test was performed at the clinic visits #1 and #3 prior to drug administration.

Following review of screening information and lab results, eligibility was confirmed. Eligible participants completed studies during the course of four visits to the Amish Research Clinic in Lancaster, PA.

Randomization: Prior to Clinic Visit #1, enrolled subjects were randomized (1:1) to either the clopidogrel or ticagrelor intervention. Clinical staff, blinded to *CES1* genotype, were notified of the order of drug intervention through the delivery of a sealed, opaque envelope from a research team member who was also blinded to participant genotype. Assignment envelopes were shuffled prior to study initiation and delivered sequentially. Participants who started with the clopidogrel intervention underwent the ticagrelor intervention after the prerequisite washout period and vice versa.

Clinic Visit #1 (Baseline Platelet Function): Research subjects were transported to the Amish Research Clinic after an overnight fast where heights, weights, and vital signs were measured. Women of childbearing age completed a pregnancy test. A catheter was placed, and fasting blood samples were obtained to assess circulating lipid levels (LDL, HDL, and triglycerides), evaluate baseline measures of agonist-stimulated platelet aggregation, and for sample banking. Participants were then observed while taking their first dose of clopidogrel or ticagrelor (based on randomization procedure), discharged to home with additional tablets, and

instructed to take the appropriate dose (75 mg/ daily for clopidogrel, 180 mg/d for ticagrelor) at the same time each day. A participant logbook was given to each participant to record their daily doses

Clinic Visit #2 (On-Clopidogrel Platelet Function): On the 7th day, subjects returned to the clinic, observed taking their last dose, and fasting blood samples were drawn 1-hour post-dose for measurement of agonist-stimulated platelet aggregation and sample banking. Drug adherence was assessed by pill count and participant logbook. Each participant then underwent a 14-day washout period to restore basal platelet function, consistent with the average lifespan of a platelet (7 – 10 days).

Clinic Visit #3 (Repeat Measures of Baseline Platelet Function): After the 14-day washout period, research subjects again were transported to the Amish Research Clinic in the fasting state where they were weighed and their vital signs measured. Reproductive age women underwent a 2nd pregnancy test. Blood samples were obtained for repeat measures of baseline platelet function and sample banking. Participants were then observed while taking their first dose of clopidogrel or ticagrelor (whichever one was not administered during the first intervention period), discharged to home with additional tablets, and instructed to take the appropriate dose at the same time each day. A participant logbook was given to each participant to record their daily doses.

Clinic Visit #4 (On-Ticagrelor Platelet Function): On the 7th day, subjects returned to the clinic, observed taking their last dose, and fasting blood samples were drawn 1-hour post-dose for measurement of agonist-stimulated platelet aggregation and sample banking. Drug adherence was assessed by pill count and participant logbook.

Assessment of Platelet Function: at each clinic visit, platelet-rich plasma (PRP) was isolated from fasting blood samples drawn into 3.2% citrate-anticoagulated tubes (Becton-Dickinson, Franklin Lakes, NJ) and platelet counts were adjusted to 200,000 platelets/ μ l using platelet-poor plasma. Platelet function was assessed by optical aggregometry using a PAP8E Aggregometer (Bio/Data Corporation, Horsham, PA) according to the manufacturer's instructions after stimulation with 20 μ M ADP and expressed as the maximal percentage change in light transmittance using platelet-poor plasma as a referent.

Distributions of summary statistics (e.g. age, sex, change in platelet function) were generated using SAS (Cary, NC). Change in clopidogrel-induced platelet aggregation in response to ADP was calculated by subtracting observed post-clopidogrel maximal platelet aggregation values from baseline (i.e. pre-drug) values. Similarly, change in ticagrelor-induced platelet aggregation in response to ADP was calculated by subtracting observed ticagrelor maximal platelet aggregation values from baseline (i.e. pre-drug) values.

The primary endpoint of this investigation was to determine within each drug group if *CES1* genotype is associated with change in platelet aggregation. Change in platelet aggregation, defined as the relative differences in platelet aggregation between baseline and day 7 of a given drug intervention, was calculated as: Change = [(MPA_{baseline} – MPA_{day 7}), where MPA = maximal platelet aggregation. Consideration of relevant biological variables that influence platelet aggregation and/or drug response were explored in our statistical models. Specifically, the effect of *CES1* genotype on agonist-stimulated change in platelet aggregation was calculated using a variance component method under an additive or dominant model that simultaneously adjusted for age, sex, body mass index (BMI), and relatedness among study participants. Relatedness among participants were accounted for by including a polygenic component as a random effect. Briefly, a model for the polygenic component was established by constructing a relationship matrix derived from the complete Amish pedigree structure available through published genealogical records maintained by the church.

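### The stated purpose is a genotype-by-drug interaction on on-treatment platelet function, but the only analysis described is of change from baseline within each drug

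*Combined protocol and SAP*

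**What the plan says.** **Purpose.** The unnumbered opening paragraph says the aggregometry was done "to assess the interaction of genotype and drug choice on on-treatment platelet function". The same sentence ties both measurements to that aim: "platelet aggregometry performed pre- and post-drug administration was performed in order to assess".

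**What on-treatment function means here.** The titles of Clinic Visits #2 and #4 label them as on-clopidogrel and on-ticagrelor platelet function. Visits #1 and #3 are labelled as baseline function. At Visits #2 and #4, on day 7, "fasting blood samples were drawn 1-hour post-dose for measurement of agonist-stimulated platelet aggregation". The platelet function paragraph expresses the visit measurement as a maximal percentage change in light transmittance, which is the MPA. On-treatment function is therefore the day-7 MPA.

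**Analysis.** The statistical paragraphs build each outcome as a difference from the pre-drug value: "subtracting observed post-clopidogrel maximal platelet aggregation values from baseline (i.e. pre-drug) values" for clopidogrel and "subtracting observed ticagrelor maximal platelet aggregation values from baseline (i.e. pre-drug) values" for ticagrelor. The primary endpoint paragraph then begins "The primary endpoint of this investigation was to determine within each drug group" and asks whether genotype "is associated with change in platelet aggregation". The model adjusts for age, sex, BMI and relatedness. Baseline MPA, drug, period and sequence are not listed. No analysis of the day-7 level is described, by genotype or between drugs.

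**The concern.** Level and change are different quantities. A genotype group can show a larger change with the same on-treatment level, or the same change with a different level, if its pre-dose aggregation differs. Nothing in the design balances pre-dose aggregation across genotype groups, because genotype is the recruitment factor and not a randomised one. Nothing in the listed covariates adjusts for it.

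The purpose also refers to an interaction of genotype with drug. Each participant takes both drugs, so the crossover gives a direct within-person comparison of the two day-7 values. The described analysis looks at each drug on its own and does not use that comparison. A reader who takes the purpose at its word would find no result that answers it.

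**Working it through.** **Inputs from the documents.** Group sizes are 17 G143E carriers, 38 rs7498748 carriers and 34 controls (17 + 38 + 34 = 89, as stated). There is one baseline and one day-7 value in each of two periods, and the outcome is baseline minus day 7. No SD, correlation, effect size or power figure is given, so there is no planned figure to reproduce. All SDs and correlations below are assumptions.

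**1. Within one drug.** Let B be baseline MPA and D day-7 MPA. For carriers versus controls:

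genotype difference in change = (genotype difference in B) − (genotype difference in D).

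If carriers start d points higher and reach the same day-7 level, the change differs by d and the level by 0. If they start d higher and end d higher, the change differs by 0 and the level by d. The described analysis cannot tell these apart.

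**2. Between drugs, within a person.** With subscripts C (clopidogrel) and T (ticagrelor):

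(B_C − D_C) − (B_T − D_T) = (D_T − D_C) − (B_T − B_C).

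A genotype difference in baseline that is stable over the two periods cancels from D_T − D_C. The change-score contrast has the same expectation if baseline is stable, but it brings in two more measurements.

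**3. Variance of the two contrasts.** Assume a common SD s, correlation rw between baseline and day 7 in the same period, and correlation rb between any two measurements in different periods.

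- Day-7 contrast: 2s²(1 − rb)
- Change-score contrast: 4s²(1 − rw)
- Ratio, change to day-7: 2(1 − rw)/(1 − rb), equal to 1 at rw = (1 + rb)/2

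| rb | rw | ratio |
|---|---|---|
| 0.5 | 0.5 | 2.00 |
| 0.5 | 0.6 | 1.60 |
| 0.5 | 0.7 | 1.20 |
| 0.5 | 0.75 | 1.00 |
| 0.5 | 0.85 | 0.60 |

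For an interaction with 80% power on the day-7 contrast (two-sided 0.05), power on the change contrast would be 51% at rw = 0.5, 60% at rw = 0.6 and 80% at rw = 0.75, with rb = 0.5 throughout. These powers are the same for 17 versus 34 and for 38 versus 34.

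**4. The same comparison in MPA points.** Take 17 versus 34, independent visit noise with SD 8, and √(1/17 + 1/34) = 0.297.

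- No person-by-drug variation: change √(4 × 64) × 0.297 = 4.75; day-7 √(2 × 64) × 0.297 = 3.36.
- Person-by-drug SD 10 on each drug: change √(256 + 200) × 0.297 = 6.34; day-7 √(128 + 200) × 0.297 = 5.38.

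The SE is about 29% smaller in the first case and 15% smaller in the second.

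**5. The analysis that is described.** Add a between-person SD of 8 to the same assumptions. Within one drug, the day-7 variance is 64 + 64 = 128 and the change variance is 2 × 64 = 128. With person-by-drug SD 10 both become 228. In general the change-to-level ratio is 2(1 − r), where r is the correlation of baseline with day 7: 1.4 at r = 0.3 and 0.6 at r = 0.7. The described comparison need not lose any precision.

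**The case against.** The strongest objection is that change is a reasonable way to put the purpose into practice. The purpose sentence names measurements before and after drug. Because genotype is not randomised, a day-7 level within one drug mixes any pre-existing genotype difference with the response to the drug, and subtraction is meant to remove the former. This stands, and it is why change should stay primary. It does not close the gap. Collecting a baseline does not make change the target, and the visit titles use on-treatment function for the day-7 value. The within-person drug difference in day-7 MPA is also free of a stable baseline difference (step 2).

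A reader might infer that the planned analysis is made less precise by two extra noisy baselines. The documents do not support that. The plan contains no within-person drug contrast, so nothing in it carries those baselines. The loss applies only to a contrast that someone might later form from the change scores, and it reverses when rw exceeds (1 + rb)/2.

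A reader might also infer that day-7 MPA was never examined. The statistical text is short and its list of summaries is given as examples. The supportable statement is that no such analysis is described.

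Finally, the endpoint is worded as "defined as the relative differences in platelet aggregation between baseline and day 7 of a given drug intervention", while the formula shown is an absolute difference with an unclosed bracket. A denominator may have been lost when the text was extracted. The variance figures apply to the absolute form only. A relative change would still not be the day-7 level.

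**Conclusion.** The mismatch is real and rests on the text alone: the purpose is a genotype-by-drug interaction on on-treatment function, and the analysis described is genotype against change within each drug. As written, the plan does not answer its stated question on the day-7 scale, and it describes no genotype-by-drug comparison on the change scale either. Change is not a wrong endpoint; the target has been left unreconciled.

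The possible discrepancy between change and level equals the genotype difference in baseline MPA, which the documents do not report. A precision gain from using day-7 values for the drug contrast is likely but conditional. The variance ratio is 2 when rw = rb and falls below 1 for strong within-period correlation, and the documents give no values to decide between these cases. The point should be corrected, but it does not invalidate the primary analysis.

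**What to change.** Keep change as the primary variable. Add a secondary analysis with these parts:

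- **Outcomes:** day-7 MPA on each drug, and the within-person difference in day-7 MPA (ticagrelor minus clopidogrel), each compared by genotype.
- **Model:** the existing one (age, sex, BMI, polygenic random effect) plus a period/sequence term. The term is needed because the randomisation paragraph describes no stratification by genotype, so drug order may be uneven across genotype groups.
- **Sensitivity analysis:** the same model adjusted for the period baselines.
- **Interpretation:** state that the interaction named in the purpose is judged on the within-person difference.
- **Status:** the document is dated March 2024 and written in the past tense. If results had already been seen, label the analysis post hoc.

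The data were already collected at Visits #2 and #4. The cost is a small amount of extra modelling, some SAP wording, and one more reported outcome.

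### The phenotyping was done to assess a genotype-by-drug interaction, but the analysis specifies only within-drug genotype tests and no test or interval for the interaction

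*Combined protocol and SAP*

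**What the plan says.** The document has few headings, so places are given by paragraph.

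- **Opening paragraph, aim.** Aggregometry before and after each drug was done "in order to assess the interaction of genotype and drug choice on on-treatment platelet function". No other scientific aim is stated there.
- **Opening paragraph, groups.** The 89 participants are "17 G143E carriers, 38 rs7498748 minor allele carriers, and 34 controls".
- **Randomization.** Order is allocated 1:1 and everyone crosses over: "Participants who started with the clopidogrel intervention underwent the ticagrelor intervention after the prerequisite washout period and vice versa".
- **Clinic Visit #3.** The second period has its own baseline: "Blood samples were obtained for repeat measures of baseline platelet function and sample banking". With Visits #1, #2 and #4, each participant therefore has a baseline and a day-7 value on both drugs.
- **Closing paragraph (under Assessment of Platelet Function).** "The primary endpoint of this investigation was to determine within each drug group if" *CES1* genotype is related to the change, where change is baseline minus day-7 maximal aggregation. The genotype effect comes from a variance-component method under an "additive or dominant model that simultaneously adjusted for age, sex, body mass index (BMI), and relatedness among study participants". The only random effect named is the polygenic one.

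**The concern.** The aim is a comparison of genotype effects between drugs. The analysis estimates the genotype effect on each drug separately and stops there. Nothing in the text supplies a genotype-by-drug term, a within-person contrast between drugs, a period or order term, or a rule for setting the two within-drug results against each other.

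Subtracting the two coefficients gives a point estimate of the interaction. It gives no valid standard error, because both coefficients come from the same people and their covariance is not estimated by two separate models. A reader who wants the interaction has two poor options:

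- Compare significance across drugs. A result that is significant on one drug and not on the other is not evidence that the effects differ.
- Combine the two standard errors as if independent. The interval is then too wide whenever a person's responses to the two drugs are positively correlated.

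A smaller mismatch is that the opening paragraph names on-treatment function, while the analysis uses change from baseline.

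**Working it through.** **Text check.** The stated aim and the stated analysis compare as follows.

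| | Opening paragraph | Closing paragraph |
|---|---|---|
| Question | Does the genotype effect depend on the drug? | Is there a genotype effect on each drug? |
| Parameter | Difference between two genotype effects | Two genotype effects, taken separately |
| Model term or interval | None given | Genotype, age, sex, BMI, polygenic effect |

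The sentence about exploring relevant biological variables does not fill the gap. The sentence after it spells out the adjustment, and drug is not in the list.

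**Inputs.** Group sizes 17, 38 and 34 are from the opening paragraph (17 + 38 + 34 = 89). The plan gives no SD, effect size, power, alpha or correlation, so there is no figure of its own to reproduce. Assumed here:

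- two-sided alpha 0.05
- equal SD of change on both drugs
- correlation rho between a person's two changes of 0, 0.3, 0.5 or 0.7
- each variant's carriers compared with the 34 controls
- relatedness and covariates ignored

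**Step 1: interval for the interaction.** Let D = change on clopidogrel − change on ticagrelor. Its SD is SD × √(2(1 − rho)). The 95% half-width for a genotype difference in D is t(0.975, n1 + n2 − 2) × √(1/n1 + 1/n2) × √(2(1 − rho)).

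- 17 v 34: 2.0096 × 0.2970 = 0.597
- 38 v 34: 1.9944 × 0.2361 = 0.4708
- √(2(1 − rho)) = 1.4142, 1.1832, 1, 0.7746 for the four values of rho

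| rho | 0 | 0.3 | 0.5 | 0.7 |
|---|---|---|---|---|
| G143E v controls, ± SD | 0.84 | 0.71 | 0.60 | 0.46 |
| rs7498748 v controls, ± SD | 0.67 | 0.56 | 0.47 | 0.36 |
| Narrowing from pairing, 1 − √(1 − rho) | 0% | 16% | 29% | 45% |

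Treating the two drugs as independent gives the rho = 0 column whatever rho is.

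**Step 2: detectable interaction at 80% power.** The two-sample t effect size is 0.85 (17 v 34) and 0.67 (38 v 34). Multiplying by √(2(1 − rho)) gives 1.20, 1.00, 0.85 and 0.66 SD for G143E, and 0.95, 0.79, 0.67 and 0.52 SD for rs7498748.

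**Step 3: the error if significance is compared across drugs.** Suppose the genotype effect is identical on both drugs. The chance that exactly one test is significant, at rho = 0, is 2 × power × (1 − power): 2 × 0.5 × 0.5 = 0.50 and 2 × 0.8 × 0.2 = 0.32. For other rho it is P(exactly one |z| > 1.96) under a bivariate normal with equal means.

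| rho | 0 | 0.3 | 0.5 | 0.7 |
|---|---|---|---|---|
| No effect | 10% | 9% | 8% | 7% |
| 50% power per test | 50% | 40% | 33% | 25% |
| 80% power per test | 32% | 27% | 23% | 17% |
| 95% power per test | 10% | 9% | 8% | 6% |

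A direct test on D rejects in 5%.

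**The case against.** The declared primary endpoint is the within-drug association, and the specified model answers it. Read literally, the purpose sentence is to conduct the crossover; the interaction appears in the next sentence, as the reason for the phenotyping. This stands as a limit on the point: the primary analysis is not defective. But the interaction is the only scientific aim in that paragraph, and it has no analysis.

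The figures rest on assumptions. The plan does not say that each variant is compared only with the 34 controls. Using all 89 participants (17 v 72 and 38 v 51), the half-widths would be 0.76/0.63/0.54/0.42 and 0.60/0.50/0.43/0.33 SD, about 10% narrower. Additive coding would give a per-allele interval, which cannot be computed without allele counts. If one drug's SD were half the other's, the pairing gain would be 1 − √(1 − 0.8 rho), or 13%, 23% and 34% at rho 0.3, 0.5 and 0.7. With rho = −0.3 and equal SDs, the paired interval would be 14% wider than the independent one, because the independent interval would then be too narrow. All of this changes the size of the illustration and leaves the gap in place.

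The plan nowhere proposes comparing p-values across drugs, so Step 3 measures a possible reader error and carries less weight. The on-treatment mismatch is also minor: the same sentence mentions measurement before and after drug, which fits change from baseline. Order was randomized, so leaving it out does not by itself bias the within-drug genotype estimates.

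**Conclusion.** The point holds. The plan states an interaction aim, collects paired data that can address it, and specifies no inference for it. It should be fixed, though it does not undermine the stated primary analysis. Under the assumptions listed, a direct interaction interval would be ±0.46 to ±0.84 SD for G143E and ±0.36 to ±0.67 SD for rs7498748 over rho 0.7 to 0; an interval that ignored the pairing would stay at the wide end. The textual finding depends on none of these assumptions.

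**What to change.** Keep the within-drug analyses as primary and add one analysis for the interaction:

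1. For each participant compute D = change on clopidogrel − change on ticagrelor.
2. Regress D on genotype in the existing variance-component model (age, sex, BMI, polygenic effect), adding treatment order.
3. Report the estimate and 95% CI for G143E and for rs7498748, each against controls.
4. Name the genetic coding, say whether the two intervals are adjusted for multiplicity, and state whether the interaction outcome is change or on-treatment aggregation.

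A joint mixed model is an alternative. It matches the regression of D only if it includes covariate-by-drug terms and a corresponding polygenic-by-drug component.

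The document is written in the past tense, so if this analysis was not prespecified, label it as added after the fact. The cost is one extra model on data already collected, plus wording, with no new participants or procedures. The drawbacks are that the interval may be wide, especially for the 17 G143E carriers, and that a late addition carries only post hoc weight.
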